Protocol	
Study Sponsor:	Canadian Immunization Research Network (CIRN)
Funding:	Canadian Institutes of Health Research/Public Health Agency of Canada, GlaxoSmithKline, Sanofi Pasteur Limited, others to be determined
Primary Study Product and numbers	Not Applicable
Other Study Product	Not applicable
Date of protocol	18 May 2021
Date of protocol amendment/administrative change	
Title	A study to evaluate pharmacists as immunizers to improve coverage and provider/recipient satisfaction
Detailed Title	Pharmacists as Immunizers to Improve Coverage and Provider/Recipient Satisfaction: A prospective, C ontrolled C ommunity E mbedded S tudy with vaccines with low coverage rates (The Improve ACCESS study)
Registration Number	NCT02868970

ORIGINAL PAGE DELETED FOR PRIVACY REASONS

ORIGINAL PAGE DELETED FOR PRIVACY REASONS

CONFIDENTIAL SYNOPSIS

- DetailedPharmacists as Immunizers to Improve Coverage and Provider/Recipient Satisfaction:TitleA prospective, Controlled Community Embedded Study with vaccineS with low
coverage rates (The Improve ACCESS study)
- **Indication** Implement and compare new community pharmacy-based strategies for improving vaccine coverage.

Rationale Although there are many safe and effective vaccines for adults, public perception of for the vaccination is that it is primarily for infants and children. The National Advisory study and Committee on Immunization (NACI) recommends adults and adolescents receive study design human papilloma virus (HPV) vaccine, influenza vaccine, zoster vaccine, tetanusdiphtheria-acellular pertussis vaccine (Tdap), meningococcal vaccine, and pneumococcal vaccine. While NACI makes recommendations, provinces and territories (P/Ts) determine if they will fund and implement vaccine programs. Unlike the childhood immunization programs which tend to be funded by P/Ts, many adult vaccines are unfunded, resulting in poor population uptake. In this project we propose to implement and compare new community pharmacy-based strategies for improving vaccine coverage. This study will provide the results to public health, which can then determine future funding strategies.

Objectives

Primary Objectives:

The proposed study has two primary objectives:

- 1. To assess the effectiveness of a bundled pharmacist-delivery strategy consisting of communication and funding strategies on vaccine coverage.
- 2. To determine pre- and post-intervention knowledge, attitudes, beliefs and behaviours (KABB) of target adults, pharmacists, physicians, and vaccine providing nurses.

Secondary Objectives:

- 1. To assess the impact of various funding models on vaccination coverage.
- 2. To evaluate a pharmacy-based strategy for recruiting participants for a patient-reported active adverse event following immunization surveillance system.

Primary Hypothesis:

 Vaccine coverage with all studied vaccines will increase significantly after implementation of the bundled pharmacist-delivery strategy. A significant increase will be defined as an increase of ≥10% vaccine coverage from pre-program levels.

Secondary Hypotheses:

1. The cost of a vaccine is a key factor in an individuals' decision-making

ROMEO File #: 1021559

with respect to vaccination. It is expected that vaccinations provided at no or minimal charge will have higher uptake than those that require more financial resources to obtain.

2. We hypothesize knowledge about the vaccines studied, high dose TIV, meningococcal B vaccine, meningococcal ACWY vaccine, and Tdap, is low among the general public, but high among practitioners. We hypothesize we will find a high level of support among both the public and health care providers for pharmacists to provide vaccines measured in our study. Knowledge and support amongst both providers and the public will increase after implementation of the program.

Study Methodology

design

This will be a two-year demonstration program implementation and evaluation project in two Canadian provinces, New Brunswick and Nova Scotia. One community in each province will be allocated to implementation strategies specifically designed for each of the target vaccines. One community in each province will serve as the non-intervention control arm where pharmacist immunization practice will continue unchanged.

Inclusion criteria for the selection of the four communities are a stable population, service by a regional hospital and community pharmacies, and lack of substantial health care spill-over to adjacent communities. Spill over is defined as a pattern of health-care utilization where patients regularly receive care at different regional health centres. Communities will be geographically separated to minimize potential spill over.

Pharmacists in intervention communities will provide vaccines through bundling of different payment mechanisms and communication strategies, depending on the vaccine. Descriptions of the various methodologies used for the study are below.

Different Payment Mechanisms

Intervention communities will provide vaccine through the following payment mechanisms, based on the study vaccine:

- 1. universal vaccination with "publicly funded" vaccine (vaccine provided to individual without charge (i.e. Tdap vaccine))
- vaccination using a co-pay model (individuals receive vaccine at no cost after paying a designated co-pay fee comprised of the pharmacy dispensing fee and any administration fee charged by the pharmacist immunizers (i.e. highdose TIV); and
- 3. vaccination using the current private market model where vaccine would be purchased either by the recipient or through insurance (standard of care control arm, (i.e. Meningococcal serogroup B, Meningococcal serogroup

ROMEO File #: 1021559

ACWY, high-dose TIV influenza, travel health vaccines, and herpes zoster vaccine).

Different Public Communication Strategies

Pharmacists and pharmacy staff in intervention communities will use various public communication strategies, including:

- 1. targeted mail outs and/or phone calls by pharmacies to individuals in their databases based on risk factors for contracting and/or transmitting vaccine-preventable disease (e.g., immunosuppressant medications, recent birth in family)
- 2. timed marketing linked to other vaccine clinics (e.g., influenza clinics) and awareness campaigns (e.g., back-to-school advertising)

The non-intervention control arm will be the current model wherein a client specifically requests a vaccination or the pharmacist offers this option while the patient is in the pharmacy.

Outcome measure:

1. Repeated Cross-Sectional KABB

KABB will be determined by public surveys in the four communities and by surveys of health care providers (pharmacists, physicians, and public health practitioners) prior to and after the two-year intervention.

2. Vaccine Coverage

Vaccine coverage (number vaccinated divided by the number eligible for vaccine) will be measured using pharmacy database analysis, public health vaccine reports by physicians, vaccine doses delivered (in all four regions), and by public survey within the study communities (part of the KABB survey). Statistics Canada census data from 2015 will be used to determine the denominator for those eligible for the vaccine by 5-year age groups.

3. Adverse Events Following Immunization Reporting (AEFI)

Using the Canadian National Vaccine Safety Network (CANVAS)'s surveillance system for adverse events following seasonal influenza vaccination, we will compare the proportions of eligible individuals who register for CANVAS and complete the online AEFI survey among pharmacies using active recruitment strategies (e.g., handing out information sheets and registration forms) and those using passive recruitment strategies (e.g., displaying posters and information sheets).

Sample Size
 There are four communities involved in the study, Saint John and Moncton, New Brunswick and New Glasgow/Pictou/Antigonish and Kentville/Wolfville/New Minas, Nova Scotia. All participating pharmacies in each community will be allocated either to the bundled pharmacist-delivery intervention or to standard care (control arm). Residents in each community will receive a KABB survey, regardless of whether or not they were vaccinated as part of this study. Information and registration forms

ROMEO File #: 1021559

for CANVAS surveillance will be actively distributed to those who received influenza vaccines in the intervention communities and information on CANVAS will be displayed at pharmacies in control communities. A sample size of 400 for the KABB survey will provide a margin of error of less than 5% for estimated proportions. For vaccine coverage, a separate sample size of 596 per group will provide power of at least 80% to detect superiority.

Endpoints Outcomes/analysis plan/sample size/statistics Outcomes

- 1. Population-specific vaccine coverage before and after programimplementation interventions.
- 2. Proportion of population in intervention districts whose supplementary health benefit plans cover studied vaccines.
- 3. Public KABB about vaccine-preventable diseases and related vaccines before and after program-implementation interventions.
- 4. Public willingness to pay and co-pay for studied vaccines.
- 5. Healthcare providers KABB regarding pharmacist- delivered vaccine programs.
- 6. Public and health care provider satisfaction with various models of vaccine program delivery.
- 7. Proportions of influenza vaccine recipients who register for CANVAS and who complete the online AEFI survey in intervention versus control communities.

TABLE OF CONTENTS	
SYNOPSIS	PAGE 4
LIST OF ABBREVIATIONS	PAGE 9
TRADEMARKS	PAGE 10
1 INTRODUCTION	PAGE 11
2 OBJECTIVES	PAGE 14
3 STUDY DESIGN	PAGE 14
4 STUDY PRODUCT	PAGE 21

APPENDIX D	
APPENDIX E	PAGE 118

CONFIDENTIAL LIST OF ABBREVIATIONS

Adult NIS	Adult National Immunization Survey
AEFI	Adverse event following immunization
CANVAS	Canadian National Vaccine Safety Network
CCfV	Canadian Center for Vaccinology
CIRN	Canadian Immunization Research Network
IWK	Izaak Walton Killam Health Centre
KABB	Knowledge, attitudes, beliefs and behaviours
NACI	National Advisory Committee on Immunization
P/T	Provinces and Territories
REB	Research Ethics Board
SAE	Serious adverse event
Tdap	Adult formulation tetanus and diphtheria toxoids and acellular pertussis vaccine
TIV	Trivalent inactivated vaccine, influenza
ТрВ	Theory of planned behaviour
4CMenB	Meningococcal B vaccine, Bexero (Novartis)
MenACWY	Meningococcal ACWY vaccine, Nimenrix (Pfizer/GSK), Menactra (Sanofi Pasteur), Menveo (GSK).
HZ	Herpes zoster
VZV	Varicella zoster virus
PHN	Postherpetic neuralgia

TRADEMARKS

Adacel[®]

Avaxim®

Bexsero®

Boostrix[®]

Engerix[®]-B

Fluad®

FluLaval Tetra®

FluMist[®]

Fluviral®

Fluzone High-Dose[™]

FluZone Quad®

Havrix®

Nimenrix®

Menactra[®]

Menveo[®]

Recombivax[®]

RedCap™

Remark®

Shingrix®

Twinrix®

Typherix®

Typhim Vi®

Vaqta®

ViVaxim®

Vivotif®

Zostavax II®

1 INTRODUCTION

Although there are many safe and effective vaccines for adults, the Public Health Agency of Canada has noted that public perception of vaccination is that it is primarily for infants and children. The National Advisory Committee on Immunization (NACI) recommends that adults and adolescents receive the influenza vaccine, tetanus-diphtheria-acellular pertussis vaccine (Tdap) and meningococcal vaccines (MenACWY, 4CMenB). As well, NACI recommends that people 50 years or older receive the herpes zoster vaccine and that Canadians who travel to high-risk areas should consider getting vaccinated to protect themselves against travel-related illnesses, such as Hepatitis A and Typhoid Fever. While NACI makes recommendations, provinces and territories (P/Ts) determine if they will fund and implement vaccine programs. Unlike most childhood vaccines, which are funded by P/Ts, many adult vaccines are unfunded, resulting in poor population uptake. We propose that lack of publically funding immunization programs for adults including public health driven promotion, is associated with the observed poor population uptake. In this project, we propose to implement and compare new community pharmacy-based strategies with different payment mechanisms and measure the effect on adult vaccine coverage for three vaccines.

1.2 Recommended and Funded Vaccines

Tdap and influenza vaccines are recommended and funded for adults in most provinces; however, uptake of these vaccines remains low according to the Public Health Agency of Canada (PHAC). Increases in influenza vaccination rates amongst adults have stagnated and Tdap coverage amongst adults is estimated to be well under 10% (Public Health Agency of Canada, 2015).

1.3 Recommended but Unfunded Vaccines (RUVs)

With the increasing number of vaccines being brought to market in recent decades and shrinking health care budgets, the list of RUVs has increased (Scheifele et al., 2014). Quadrivalent meningococcal conjugate vaccine (MenACWY) and meningococcal serogroup B vaccine are recommended where regional epidemiology supports their use; however, there are differences in funding between regions. While NACI recommends influenza vaccines for all or some adults, high dose TIV for individuals ≥65 are not routinely funded. Herpes zoster (HZ) is another recommended vaccine for all Canadians who are 50 years of age or older; however, despite this recommendation, Ontario is the only province in Canada that covers the cost of Zostavax II for its residents between 65 and 70 years of age. To prevent travel-related illness, NACI recommends that Canadians get vaccinated against common food and water borne illnesses, such as Hepatitis A and Typhoid fever, as well as blood borne diseases, such as, Hepatitis B, before they travel. Although Canadians visiting certain destinations are recommended to get vaccinated, these vaccines are not publicly funded for Canadian travellers.

1.4 Reasons for Low Vaccine Coverage and Interventions to Improve Coverage

Barriers to achieving high vaccination rates are multifactorial. Some of the most common barriers to vaccination include lack of education about vaccines and vaccine-preventable diseases, lack of infrastructure to deliver vaccines, lack of access to vaccines, financial concerns, and the attitudes of clients and providers toward vaccination (Colgrove, 2007). Briss et al. (2000) found that interventions for improving vaccine coverage can be categorized as those that: a) increase community demand for vaccinations (client education, client reminders, community educational messages through media,

ROMEO File #: 1021559

money or discount coupons); b) Enhance access to vaccinations by reducing client-out-of-pocket expenses (providing insurance coverage or reducing co-payment) or expanding access in healthcare settings (reducing the distance from the setting to the population; increasing or changing hours during which vaccination services are provided; delivering vaccinations in clinical settings where they were previously not provided) or reducing administrative barriers to obtaining vaccination services within clinics (developing a "drop-in" clinic or an "express lane" vaccination service); c) improve provider behavior (educating providers about the vaccine, creating standing orders to remind them, implementing electronic systems to remind them or using a feedback system which evaluates the provider's performance). Briss et al.'s systematic review examined promotion of influenza and pneumococcal vaccines and found that interventions that enhanced access to vaccination services were far more effective than those that did not include them. In other words, use of (a) and (b) or (b) and (c) was significantly more effective than (a) and (c).

1.5 Pharmacists as Immunizers

Patients are typically educated about preventative health care during face-to-face visits with physicians in office settings, or in the case of vaccines, by nurses at vaccination appointments. The ability to educate and deliver preventative health care is limited by the available provider time during client visits. Providers note that the time to provide vaccine education is considerable, and clients' acute needs and current disease management generally take priority. New delivery models and a means of extending preventative health care delivery outside of traditional face-to-face office visits are needed (Yarnall, 2003).

Pharmacists are in a unique position of being among the most accessible of health professionals (Canadian Pharmacists Association, 2012). In a study of the attitudes and beliefs of the Canadian public on routine immunization by pharmacists, pharmacists were identified as a trustworthy source of health information, similar to public health officials and exceeded only by family doctors and nurses (MacDougall et al., 2016). Given their extended operating hours, accessibility, and established trust with patients, pharmacists are well-positioned to improve vaccination rates and health system efficacy through injection administration (Houle, 2013) Moreover, people regularly visit community pharmacies for their health care needs, particularly in rural settings, due to extended hours and convenient locations (Kau, 2011). In addition, through their interaction to fill prescriptions and education patients about their use, pharmacists have regular contact with high-risk individuals and are able to proactively and systematically review patients' medical histories and medications, and remind them about the benefits of vaccination. Such interventions have been shown to have a significant impact on a person's decision to be immunized, similar to the impact of a recommendation from a physician or nurse (Grabenstein, 1992).

Several studies from the United States have evaluated immunization rates before and after pharmacists were allowed to administer vaccines and revealed significant increases in coverage rates (Grabenstein, 1999; Steyer, 2004). Grabenstein and colleagues compared vaccination coverage rates in states where pharmacists were allowed to immunize with states where they could not. Between 1995 and 1999, vaccination coverage increased by 10.7% in states where pharmacists could administer the vaccine and 3.5% in states where they could not (p<0.05) (Grabenstein, 1999).

As of 2016, legislation has passed in nine Canadian provinces that allow pharmacists to provide immunizations to adults (as well as adolescents and children over the age of 5 in some provinces). There have been limited studies on the impact of this expansion of the professional role of pharmacists on the knowledge, attitudes, beliefs and behaviours (KABB) of the general public and other

ROMEO File #: 1021559

immunization providers regarding this change to the immunization landscape in Canada, and no published comparative implementation studies.

1.6 Previous Related Work by Team Members

Team members from the Maritime Provinces, British Columbia and Ontario have undertaken research related to pharmacist-delivered vaccination of various vaccines.

A survey completed across Canada found that pharmacists were willing to incorporate immunization into their practice and that pharmacists thought that adding vaccine administration to their scope of practice would increase public access, improve coverage rates, and be acceptable to the public (Edwards, 2015). A 2010 national survey of physicians, nurses, pharmacists and the general public to assess KABB around the delivery of Tdap and other adult vaccines revealed that greater than 50% of those surveyed would support the expansion of pharmacists' scope of practice to include adult vaccination. Perceived benefits of pharmacists providing immunizations included sharing of the time required to immunize, and enhanced record keeping (MacDougall, 2015).

Pharmacist-based immunization strategies for influenza vaccination were evaluated in small rural communities in interior and northern British Columbia in a 2-year, community cluster-randomized trial. In the intervention communities, pharmacy-based influenza vaccination clinics were held, and were promoted to eligible patients using personalized invitations from the pharmacists; invitations distributed opportunistically by a pharmacist to eligible patients presenting to pharmacies during the flu season, and community-wide promotion using posters and the local media. The mean influenza immunization rate in the control communities (n=15) was 56.9% (SD 28.0) and 80.1% (SD 18.4) in the intervention communities (n=14) (p=0.01) for those \geq 65 years of age (Marra, 2014).

In New Brunswick, legislation has enabled pharmacists with proper certification to immunize since 2009. There are limited data about the experiences of Canadian pharmacists as vaccine providers. We are currently analyzing a survey administered to pharmacists in New Brunswick to examine demographics and KABB around immunization. The survey has contributed to the design of the health care provider survey proposed for this project.

OPEN (Ontario Pharmacy Research Collaboration) is conducting a series of studies to examine the impact of the scope of practice change that allowed pharmacists to administer the influenza vaccine for the 2012/13 and 2013/14 influenza seasons. Impact on Ontario immunization rates will be measured using pharmacist and MD billing and public health clinic data. Patient demographic and health data will be used to explore uptake in high-risk populations and demographic and regional differences. Researchers will survey Ontario pharmacists to gauge their attitudes on influenza immunization and determine their readiness stage, facilitators and barriers to implementation and recommendations for system changes. Patient perspectives will be examined broadly via provincial survey. Focus group sessions with physicians and nurses will examine their perceptions of pharmacist-administered flu shots, as well as related issues and challenges.

The first year of that pharmacists participated as immunizers in the universal influenza vaccine program in Nova Scotia, there was an increase in both the number of influenza vaccines administered overall and in influenza coverage rates compared to the previous three influenza seasons. Nova Scotia pharmacists administered 78,102 influenza vaccines in the 2013-2014 season, contributing to an increase of 15.8% in

the total number of influenza vaccines administered compared to the previous flu season, when they were not yet regulated and funded to administer injections (Isenor, 2016)

2 OBJECTIVES

2.1 Primary Objectives

The proposed study has two primary objectives:

- 1. To assess the effectiveness of a bundled pharmacist-delivery strategy consisting of communication and funding strategies on vaccine coverage.
- 2. To determine the increase in pre- and post-intervention knowledge, attitudes, beliefs and behaviours (KABB) of target adults, pharmacists, physicians, and public health practitioners.

2.2 Secondary Objectives

- 1. To assess the impact of various funding models on vaccination coverage.
- 2. To evaluate a pharmacy-based strategy for recruiting participants for a patient-reported active adverse event following immunization surveillance system.

2.3 Primary Hypothesis:

 Vaccine coverage with all studied vaccines (high dose TIV, meningococcal B vaccine, meningococcal ACWY vaccine, Tdap, herpes zoster vaccine, and travel health vaccines) will increase significantly after implementation of the bundled pharmacist-delivery strategy. A significant increase will be defined as an increase of ≥10% vaccine coverage from preintervention levels.

2.4 Secondary Hypotheses:

- 1. The cost of a vaccine is a key factor in the individual's decision to be vaccinated. It is expected that vaccinations provided at no or minimal charge will have higher uptake than those that require more financial resources to obtain.
- 2. Knowledge about the vaccines studied is low among the general public, but higher among practitioners. There is a high level of support among both the public and health care providers for pharmacists as immunizers. Knowledge and support amongst both providers and the public will increase after implementation of the program.

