determined by physician billing data and public health provision of vaccine to physicians relative to the Statistics Canada population age specific census data for that community. A study-specific system of reciprocal notification forms for family doctors will be implemented that is similar to that used for publicly funded routine vaccines. A third estimate of vaccine coverage will be vaccine doses distributed in the participating communities (obtained from the manufacturer) relative to the eligible population based on Statistics Canada census data (2011 and 2016 when available). The fourth estimate of vaccine coverage will be derived from the pre- and postprogram public survey. Binomial point estimates and confidence intervals will be made for vaccine coverage rate within site, and coverage will be compared between and among sites using confidence intervals for the difference of binomial proportions, Fisher's exact tests, and logistic regression. Using a margin of superiority of 10%, when comparing two coverage proportions within site or between sites, a sample size of 298 per group gives 80% power to conclude in favor of superiority when the true difference in proportions is at least 20%, and a sample size of 1209 per group provides 80% power when the true difference in proportions is at least 15%, assuming independent responses. However, it is anticipated that there will be dependence within the family unit regarding the decision to be vaccinated, in which case the precision on the binomial point estimate, and thereby, the required sample size, depends on the size of the family unit and the intraclass correlation. Assuming the family unit to consist of two adults, and under the worst-case scenario in which the decision on vaccination is fully concordant for the two family members, the required sample size per group to detect a specified difference is doubled, to 596 (2418) when the true difference is at least 20% (15%). Estimates of the intraclass correlation will be calculated using data from pharmacy databases and from the public survey portion of the study, and these will be used to adjust confidence intervals and test statistics to accommodate within family dependence (Donner, Brikett, & Buck, 1981).

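### The stated 80% power is for one vaccine comparison, not for the primary hypothesis that coverage rises by at least 10% for all six vaccine groups; joint power is not given.

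*Combined protocol and SAP*

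**What the plan says.** Section 2.3 gives the primary hypothesis as a statement about every study vaccine: "Vaccine coverage with all studied vaccines (high dose TIV, meningococcal B vaccine, meningococcal ACWY vaccine, Tdap, herpes zoster vaccine, and travel health vaccines", all expected to increase significantly. The criterion follows: "A significant increase will be defined as an increase of ≥10% vaccine coverage from preintervention levels". The synopsis states its primary hypothesis over all studied vaccines too, without listing them there. Section 3.1 repeats the 10% criterion without saying that it applies to every vaccine.

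The coverage part of section 6.2 bases its power calculation on a single comparison of two coverage proportions, made within one site or between two, with a 10% superiority margin. For a true difference of 20% it states that "a sample size of 298 per group gives 80% power to conclude in favor of superiority". At a true difference of 15% it gives 1209 per group. Both are doubled, to 596 and 2418, for two-adult families whose decisions agree fully. The synopsis carries over the 596 and power of at least 80%, without saying that this is for a single comparison.

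The visible coverage text gives no joint power, no rule for combining vaccines, no correlation between vaccine results, no assumed coverage rates and no significance level for coverage.

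**The concern.** Read literally, section 2.3 holds only if all six groups meet the criterion. One vaccine short of 10% contradicts it. The power in section 6.2 answers a different question: how likely one comparison is to succeed. A requirement that all succeed needs no multiplicity correction, but it costs power, because the chance that six tests all succeed is at most the chance that the weakest one does.

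A reader of the synopsis would take 80% as the trial's chance of confirming its primary hypothesis. If that chance is materially lower, a failure to confirm the hypothesis could be read as evidence against the bundled strategy when it was a likely result even of a strategy that worked as assumed.

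**Working it through.** **Inputs from the documents.** Six vaccine groups, counting travel vaccines as one (section 2.3). Superiority margin 10%, power 80%, 298 per group at a true difference of 20%, 1209 at 15% (section 6.2). Tdap coverage estimated below 10% (section 1.2). Communities of about 30,000 adults (section 3.1).

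**Assumptions, because the documents are silent.** The 10% is absolute, as in section 6.2. One-sided alpha is 0.05 and rates are centred on 50%; both are inferred because they reproduce the stated sizes. The correlation between vaccine results is varied from 0 to 1.

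**Step 1: reproduce the plan's figures.** With unpooled variance,

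n = [p1(1−p1) + p2(1−p2)] × (z_alpha + z_beta)² / (d − 0.10)²

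where (1.645 + 0.842)² is 6.183 before rounding.

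- d = 0.20 (40% v 60%): 0.48 × 6.183 / 0.01 = 296.8, so 297 against the stated 298. Power at 298 is 80.1%.
- d = 0.15 (42.5% v 57.5%): 0.48875 × 6.183 / 0.0025 = 1208.7, so 1209, as stated.
- One-sided alpha 0.025 gives 377 and 1535, which do not match.

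The plan's sizes are right for one comparison. Rates centred on 50% are close to the largest possible variance.

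**Step 2: joint power at exactly 80% per vaccine.** With independent results, joint power is 0.8^6 = 0.262. With a common correlation rho, it is the integral over a standard normal x of Φ((0.842 + √rho·x)/√(1−rho))^6.

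| rho | all six succeed |
|---|---|
| 0 | 26% |
| 0.3 | 39% |
| 0.5 | 48% |
| 0.8 | 62% |
| 0.9 | 68% |
| 1 | 80% |

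Simulation gave 47.8% at 0.5 and 61.6% at 0.8. For 80% joint power with independent results, each vaccine needs 0.8^(1/6) = 96.3%. That is 568 per group (1136 after doubling) at a 20-point difference, or 2311 (4622) at 15 points.

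**Step 3: how far this depends on the assumptions.** At 298 per group, single power is Φ((d − 0.10)/SE − 1.645), with SE = √{[p1(1−p1) + p2(1−p2)]/298}. Here every vaccine has the same true rise.

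| baseline | true rise | one vaccine | all six, rho 0 | all six, rho 0.8 |
|---|---|---|---|---|
| 40% | 20 points | 80% | 26% | 62% |
| 10% | 20 points | 93% | 66% | 84% |
| 5% | 20 points | 97% | 84% | 92% |
| 40% | 15 points | 34% | 0.2% | 15% |
| 10% | 15 points | 50% | 1.5% | 27% |
| 5% | 15 points | 60% | 4.6% | 37% |

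If only one vaccine gains 15 points while the other five have 80% power each, independent results give 0.8^5 × 0.341 = 0.328 × 0.341 = 11%.

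**Step 4: larger denominators.** With 1,000 independent people per group, rates near 50% and a 20-point rise, SE = √(0.48/1000) = 0.0219. Single power is Φ(0.10/0.0219 − 1.645) = 99.8%, and 0.998^6 = 99%. With 3,000 per group and the doubling for families, a 15-point rise gives 87% for one vaccine and 0.870^6 = 43% for six. A vaccine whose true rise is exactly 10 points succeeds about 5% of the time at any sample size.

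**The case against.** The strongest reply is that 26% to 62% is not a property of this trial, and that stands. A reader might infer from Step 2 that the trial has at most 62% power. That needs exactly 80% per vaccine and a correlation no higher than about 0.8, and the documents fix neither. The study targets low-uptake vaccines, and the stated sizes match rates near 50%, so per-vaccine power could exceed 80% if a 20-point rise occurs.

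It also stands that 298 or 596 mainly limits the survey estimate. Three of the four coverage estimates in section 6.2 come from pharmacy, physician or distribution counts, with much larger denominators. If the 10% were only a rule on the observed rise, each vaccine would pass with about 99% probability at 298 per group and a true 20-point rise, and all six with about 96% if independent. The superiority margin in section 6.2 points to a test instead.

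These replies mostly suppose that every vaccine gains 20 points. Section 2.4 expects uptake to depend on cost, and section 3.1 lists meningococcal, zoster and travel vaccines under the private-market mechanism. A smaller gain for one of them would cap the joint power.

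Three stronger readings are not supported:

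- *No per-vaccine success rule exists.* Section 3.1 sends the reader to the appendices for vaccine-specific outcomes, and those pages were removed. A rule may be there.
- *The vaccine set is undefined, so success can be chosen after the data are seen.* The introduction does say "measure the effect on adult vaccine coverage for three vaccines". The four-vaccine list in the synopsis belongs to a secondary hypothesis about "knowledge about the vaccines studied, high dose TIV, meningococcal B vaccine, meningococcal ACWY vaccine, and Tdap", while the synopsis payment list names all six groups. Making the lists agree is editorial. An all-must-succeed rule, if that is what is meant, leaves no such freedom.
- *A single primary vaccine is needed.* That is a trade-off which would demote five of six groups in a study of a bundled strategy. The mismatch does not require it.

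**Conclusion.** The point holds in a limited form. The primary hypothesis covers six vaccine groups jointly, and the stated 80% belongs to one comparison of two proportions. At that 80% per vaccine, joint power is 26% if results are independent, about 48% at correlation 0.5, about 62% at 0.8, and 80% only if the six results move together perfectly. These figures rest on an assumed equal correlation and, for the 80% itself, on inferred rates near 50% and one-sided alpha 0.05.

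The actual joint power cannot be fixed from the documents. At 298 per group it runs from 66% to 92% for baselines of 5% to 10% with a 20-point rise throughout, and from 0.2% to 37% for the 15-point cases shown. The mismatch between hypothesis and power statement is firm; the size of the shortfall is not.

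**What to change.** In the synopsis and section 6.2, label 80% as the power for a single vaccine comparison at the stated true difference. Then take one of two routes:

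- **Keep the all-vaccines hypothesis.** State its joint power, with the expected baseline coverage and rise for each vaccine, a range of correlations, and the coverage estimate to which the sample size applies. Possible wording: joint power at 80% per vaccine would be 26% if results are independent, about 62% at correlation 0.8, and at most 80%.
- **Judge each vaccine separately.** Reword section 2.3 and the synopsis to say so, and give power per vaccine on that basis. Any rule already in the appendices should be repeated there.

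The cost is a few sentences and a short calculation from expected baselines; no new data are needed. On the first route, the printed power may fall below 80%. On the second, the claim becomes a set of separate vaccine results.
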